Regional anesthesia has been believed as one of the formats for effective perioperative pain control. Regional blocks using ultrasound-guide has become a perfect supplement to general anesthesia for extending analgesia after modified radical mastectomy. The advantage includes post-operative pain relief prolongation, a decrease in analgesic requirement post-operatively, a reduction in

nausea and vomiting scores and probability for ambulatory discharge and hospital stay (**Mohamady et al., 2019**).

The complex innervation of breast tissues poses a great challenge for the anesthesiologists to provide adequate perioperative analgesia by ultrasound guided regional blocks. Thoracic epidural, interscalene brachial plexus block, paravertebral block, pectoral nerve I and pectoral nerve II blocks have been used in different studies with good results. There are also technically simple regional blocks as ultrasound-guided Serratus anterior Plane (US-guided SAP) block and erector spinae plane (US-guided ESP) block which can be used effectively for this purpose (**Singh et al., 2019**).

Forero et al. described ultrasound-guided Erector Spinae Plane (US-ESP) block as a novel analgesic technique in which local anesthetic injection is done beneath the erector spinae muscle (**Forero et al., 2016**). Previous studies reported effective postoperative pain reduction with ESP block after radical mastectomy surgery. Nevertheless, few studies have compared the efficacy of ESP block with another block technique. (**Gad et al., 2019**).

The Serratus Anterior Plane block (SAP) provides anterolateral and partial posterior thoracic wall analgesia, affecting dermatomes from T2 to T9. SAP is affecting predominantly the lateral cutaneous branches of the thoracic intercostal nerves, along with intercostobrachial, thoracodorsal and long thoracic nerves. The block is performed further posteriorly and caudally than Pectoral Nerve Block-2, where the target nerves are located between the serratus anterior and the latissimus dorsi muscles. (**Blanco et al., 2013**)

Rationale

Modified radical mastectomy is one of the commonly performed breast surgery. Postoperative pain following mastectomy should be minimised, as in a number of women it may chronically persist for months in the form of postmastectomy pain syndrome.

Morphine administration for acute pain after mastectomy surgery has many side effects. Regional block techniques as paravertebral block and thoracic epidural anaesthesia has possible complications and technical difficulties.

The new alternative regional techniques such as erector spinae plane block and serratus anterior plane block are clinical trials for providing a safe, easy and painless anesthetic procedure with good hemodynamic and recovery profile with adequate perioperative analgesia for a large section of patients undergoing mastectomy operation in order to reduce opioids consumption and subsequently avoid opioid-related adverse effects.

Research question

Is there difference between the Ultrasound-Guided Erector Spinae Plane Block and the Serratus anterior plane Block in providing peri operative analgesia for patients undergoing Modified Radical Mastectomy?

Hypothesis

Null hypothesis (H₀):

There is no difference between Ultrasound-Guided Erector Spinae Plane Block and Serratus anterior plane Block in providing peri operative analgesia for patients undergoing Modified Radical Mastectomy under general anesthesia.

Alternative hypothesis (H₁):

There is difference between Ultrasound-Guided Erector Spinae Plane Block and Serratus anterior plane Block in providing peri operative analgesia for patients undergoing Modified Radical Mastectomy under genera anesthesia.

Aim of the work

To compare between Ultrasound-Guided Erector Spinae Plane Block and Serratus anterior plane Block for peri operative analgesia in patients undergoing Modified Radical Mastectomy operations under general anesthesia.

Objectives

To:

- Assess sensory block (onset, quality and duration) of both erector spinae plane block and serratus anterior plane block and detect which of them gives better analgesia.
- Assess post operative static and dynamic pain.
- Assess the time of first analgesic requirement post Modified Radical Mastectomy surgery.
- Detect the presence of side effects with general anesthesia.
- Assess patient satisfactions.

Patients And Methods

1- Technical design:

- **Site of the study:**

The study will be conducted in operating room in Zagazig University Hospitals.

- **Duration of the study:**

The study will be conducted over two years.

- **Sample size:**

Assuming that the mean \pm standard deviation of time of first analgesia requirement in erector spinae block group is 416 ± 108.2 minute and that in serratus anterior block is 343 ± 99.7 minute (Eldemrdaش et al., 2019), so sample size is calculated by open EPI programme to be 75 cases (25 cases in each group) with confidence level of 95% and power of test 80%.

Inclusion criteria:

- Written informed consent from the patient.
- Age: 21 – 60 years old.
- Gender: female patients.

- Body mass index: < 35 kg/m².
- Physical status: ASA grade I-II (American society of anesthesiologists).
- Type of operation: unilateral modified radical mastectomy operation.

Exclusion criteria:

- Patient with known history of allergy to study drugs.
- Chronic use of analgesics or drug dependence.
- Patients not able to understand pain assessment test.
- Anatomical abnormalities.
- Neuropathic disease.
- Pregnancy or breast feeding.
- Other contraindication of regional anesthesia e.g. septic focus at site of injection.
- patient with coagulopathy or on anticoagulant therapy.

- **Tools of data collection :**
 - Anesthetic sheet to all patients.
 - Intra operative assessment of vital signs by the anesthesiologist.
 - Post-operative assessment of pain, use of systemic analgesics and patient satisfaction in ward.

2- Operational design:

- **Type of the study:** prospective comparative randomized controlled clinical study.
- **Randomization:**

A computer-generated table will be used to divide patients equally into 3 study groups.

- **Group C (Control group) (n=25)** patients will receive only general anesthesia for Modified Radical Mastectomy.
- **Group E (n=25)** patients will receive Ultrasound-Guided Erector Spinae Plane Block before induction of general anesthesia for Modified Radical Mastectomy.
- **Group S (n=25)** patients will receive Ultrasound-Guided Serratus anterior Block before induction of general anesthesia for Modified Radical Mastectomy.

- **Equipment needed for technique:**
 - High frequency linear transducer ultrasound.
 - 22 gauge spinal needle 10 cm length.
 - Local anesthetic: bupivacaine 0.25% (for the erector spinae plane block and serratus plane block) and lidocaine 1% (for local infiltration at the site of injection).
 - Sterile preparation for the site of needle insertion, equipments and anesthesiologist.

All Cases Will Undergo:

The process

- **Patient Examination:**

- All participating patients will be interviewed preoperatively during their preoperative preparation. The goal and endpoints of the study

will be discussed. Understanding of the block will be reviewed and emphasized, informed consent will be taken.

- On physical examination, special attention will be given to document vital signs, cardiac, chest condition and exclude contraindications.
- All patients will be investigated by complete blood count, Liver functions test, kidney functions test and coagulation profile.

Steps of Performance:

- *Preparation:*
 - All patients will be kept fasting for minimum 6 hours before the operation.
 - All patients will be clinically examined in the preoperative period and routine investigations will be checked and at the same time, whole procedure will be explained. Ten centimeters visual analog scale (VAS) (**Metwally et al., 2016**), (0 – no pain and 10 – worst pain imaginable) will be also explained during preoperative visit.
 - The monitors attached included non-invasive blood pressure (NIBP), electrocardiography (ECG), and pulse oximetry.
 - An 18 G I.V cannula will be secured in the opposite hand and fluid will be started. supplemental oxygen will be administered at 6 to 8 L/min via face mask. Procedural sedation will be provided intravenously by midazolam 0.03 to 0.04 mg/kg, as needed

- **Technique:**

- **Erector Spinae Plane Block:**

Position

sitting position

Type of needle

Using 22 gauge spinal needle 10 cm length.

Scanning

Linear ultrasound probe is placed in a longitudinal parasagittal orientation 3 cm lateral to the T5 spinous process.

The erector spinae muscle is identified superficial to the tip of The T5 transverse process.

Needle insertion

The needle is inserted in- plane superior to inferior approach. The tip of the needle is placed into the fascial plane on the deep aspect of erector spinae muscle.

The location of the needle tip is confirmed by visible normal saline fluid spread separating erector spinae muscle off the bony shadow of the transverse process on ultrasonographic imaging .

Local anesthetic and volume

Injection of 20 ml of bupivacaine 0.25 %. (Singh et al., 2019)

II. Serratus Anterior Plane Block:

Position

The patient lies supine with placing the ipsi-lateral upper limb in abduction at 90° position.

Type of needle

Using 22 gauge spinal needle 10 cm length.

Scanning

After skin sterilization, Ultrasound device with high frequency [9-12] and superficial linear probe that is first placed inferior to the middle of the clavicle and moved laterally and downward to locate the 1st rib where pectoralis major and pectoralis minor muscles are identified at this US window.

The US probe is moved toward axilla till serratus anterior muscle is identified above 2nd, 3rd and 4th ribs. The transducer is held at a slightly oblique angle at the level of the 4th and 5th rib, with the upper edge supero-anterior and the lower edge infero-anterior.

Needle insertion

After infiltration of the skin at puncture site with 3 ml of lidocaine 1%, the needle is inserted inplane between the anterior serratus and the latissimus dorsi muscle on the mid-axillary line.

Local anesthetic and volume

Injection of 20 mL of 0.25% bupivacaine. (**Khemka et al., 2019**)

Assessment of block:

Onset time of sensory block

Time between injection of the drugs and loss of pin prick sensation in operating field, pin prick test done with sterile 25G needle.

Quality of sensory block will be graded as :

- Grade 0 : normal sensation
- Grade 1: loss of sensation to pinprick.
- Grade 2: loss of sensation to light touch (**Swami et al., 2012**).

Duration of sensory block

Time between onset of sensory block to the first report of postoperative pain at the surgical site that is **VAS score >3**, with first analgesic requirement by the patient.

The patients will be delivered to the operating room to receive general anesthesia with good monitoring.

General anesthesia:

- It will be standardized for all patients.

- Fentanyl 2 mcg/kg, propofol 2 mg/kg will be intravenously administered, followed by cisatracurium 0.15 mg/kg to facilitate endotracheal intubation with a suitable size of endotracheal tube.
- Lungs will be ventilated by pressure controlled mode to maintain normocapnia ($\text{PaCO}_2 = 35\text{-}45 \text{ mmHg}$) and isoflurane/O₂ mixture will be administered.
- Concentration of the inhalational agent will be 1.2 MAC of isoflurane, Heart rate and mean arterial blood pressure will be recorded every 10 minutes.
- Incremental doses of fentanyl can be given in inadequate analgesia {presented by tachycardia and hypertension (mean arterial blood pressure) $>20\%$ from baseline} after exclusion of other causes}, total amount of fentanyl consumption intraoperative will be calculated.
- Paracetamol 15ml/kg will be administered by iv infusion to all patients.
- After completion of the surgery, inhalational anesthesia will be stopped and the patient will receive neostigmine (0.05 mg/kg) and atropine sulphate (0.01 mg/kg).

Postoperative:

- After recovery from anesthesia, the patient will be transferred to the post-anesthesia care unit.
- All patients will receive paracetamol as standard intravenous infusion analgesia at dose of 15mg/Kg every 8 hours (maximum dose: 4 g / day).
- Pain will be observed and recorded using the pain assessment on a 0-10 cm line [visual analogue scale (VAS) (**Metwally et al., 2016**); 0=no pain, 1 to 3 = mild pain, 4 to 6 = moderate pain, 7 to 10 = severe pain].

- The pain is measured both at rest and movement (arm movement of 90° and sitting from lying down position) after explanation of the procedure to the patient at 2,4,8,12,18 & 24 hours after surgery by an observer blinded to treatment groups.
- All patients will be assessed for the time to first rescue analgesic and when the patient suffer from pain at score equal or above 3 on VAS, the patient will receive morphine (dose: 0.1 mg/kg intravenous as initial dose then 0.025 to 0.05 mg/kg every 5 minutes till the pain is relieved not exceeding 4 mg/h). Total morphine consumption will be calculated.
- Post-operative nausea and vomiting will be noticed, recorded using a categorical scoring system (0 = none, 1 = mild, 2 = moderate, 3 = severe) and treated, Ondansetron 4 mg IV will be administered in case of reported nausea and/or vomiting.
- Patient satisfaction will be assessed post operatively using satisfaction score (4= excellent, 3 = good, 2 = fair and 1 = poor) (**Ross et al., 2009**).

Complications and side effects:

It may include failure of the block, intra-muscular hematoma, pleural perforation, Post-operative nausea and vomiting (PONV), sedation and respiratory depression. These complications will be observed and recorded.

Data collection:

From each patient the following data will be collected upon admission:

1-Demographic data:

- Name
- Age
- Body Mass Index
- Hospital diagnosis
- Date of admission in hospital
- Medical and past history

- ASA grade I-II
- Type of operation : unilateral mastectomy surgery
- Duration of operation

2-Sensory block assessment: onset, quality of sensory block, duration of the block.

3-Hemodynamics (HR, Mean Arterial Bl.Pr), total intra-operative fentanyl consumption.

4-Static and dynamic pain scores (VAS) at 2, 4, 8, 12, 18 and 24 hours post-operatively.

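### The hypothesis names no outcome, and the first objective picks the better block on measures other than the one the trial was sized for

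*Protocol*

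**What the plan says.** Protocol, Hypothesis: the null is "There is no difference between Ultrasound-Guided Erector Spinae Plane Block and Serratus anterior plane Block in providing peri operative analgesia" and the alternative is "There is difference between Ultrasound-Guided Erector Spinae Plane Block and Serratus anterior plane Block in providing peri operative analgesia". Both concern analgesia as a general construct. The alternative has no direction.

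Protocol, Objectives: the first bullet covers onset, quality and duration of sensory block and adds that the trial will "detect which of them gives better analgesia". The second bullet is postoperative pain at rest and on movement. The third is "Assess the time of first analgesic requirement post Modified Radical Mastectomy surgery". The bullets are not ranked.

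Protocol, Sample size: the calculation uses "time of first analgesia requirement in erector spinae block group" (mean 416, SD 108.2 minutes) against 343 (SD 99.7) minutes for the serratus block. It arrives at 25 per group, "with confidence level of 95% and power of test 80" per cent.

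Protocol, Data collection: the list includes the three sensory block measures, intraoperative fentanyl, "Static and dynamic pain scores (VAS) at 2, 4, 8, 12, 18 and 24 hours post-operatively", time to first rescue request and 24-hour morphine. No outcome is designated primary. The Results section refers only to standard statistical methods.

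**The concern.** Three parts of a protocol should point to the same quantity: the hypothesis, the objective that decides the question, and the outcome behind the sample size. Here the hypothesis points to no measured quantity. The only sentence that says how the better block will be identified is attached to sensory block. The sample size is attached to time to first analgesic.

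What is at stake is the trial's conclusion. Suppose time to first rescue shows no difference between the blocks, but onset is faster with one of them, or one pain reading out of 12 differs. Under the first objective as worded, that could be presented as showing which block gives better analgesia and as a rejection of the null. A reader would have no text in the protocol with which to contest it. The error rate and power quoted in the sample-size sentence would say nothing about that claim.

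**Working it through.** **1. Set the passages side by side.**

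| Place in Protocol | Outcome it rests on |
|---|---|
| Hypothesis (H0, H1), Aim | none named; analgesia in general |
| Objectives, first bullet | sensory block onset, quality, duration |
| Objectives, third bullet | time to first analgesic requirement |
| Sample size (95%, 80%) | time to first analgesic requirement |

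Block duration partly overlaps with the sizing outcome. Under Assessment of block it runs from sensory onset to the first pain score above 3 with an analgesic requirement. Under Postoperative, rescue is triggered at a score equal to or above 3. The third objective places the first analgesic requirement after surgery, whereas sensory onset is assessed before general anesthesia. The end event is nearly the same, but the start and the cut-off differ.

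**2. Count the comparisons of Group E with Group S that bear on analgesia** (Data collection): 3 sensory block + 1 fentanyl + 2 conditions × 6 times = 12 pain readings + 1 time to first rescue + 1 morphine = 18.

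**3. Chance of at least one false rejection**, if each is tested two-sided at 5% without adjustment and any one suffices.

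- Independence: 1 − 0.95^18 = 0.603.
- Equally correlated normal test statistics (the correlations are assumptions; the documents give none):

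| Common correlation | 18 tests | 8 tests |
|---|---|---|
| 0 | 60% | 34% |
| 0.3 | 51% | 30% |
| 0.5 | 40% | 25% |
| 0.7 | 28% | 19% |
| 0.9 | 15% | 12% |

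The 8-test column treats pain at rest and pain on movement as one repeated-measures series each (3 + 1 + 2 + 1 + 1 = 8). With a single named outcome the figure is 5%.

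**4. What the sized outcome can carry.** Difference: 416 − 343 = 73 minutes. Pooled SD: √((108.2² + 99.7²)/2) = √10823.7 = 104.04. Formula: n per group = 2 × [SD × (z_α + z_power) / difference]².

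- Two-sided 5%, 80% power: 2 × [104.04 × (1.960 + 0.842)/73]² = 31.9, so 32 per group. This does not reproduce the stated 25.
- One-sided 5%, 80% power: 2 × [104.04 × (1.645 + 0.842)/73]² = 25.1, so 26 per group, close to the stated 25.
- Two-sided power at 25 per group: 73 / (104.04 × √(2/25)) = 2.481; 2.481 − 1.960 = 0.521, giving 69.9% (68.1% with the t distribution).

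The stated size therefore fits a one-sided calculation, while the alternative hypothesis has no direction.

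**The case against.** The strongest reply is that time to first analgesic is the only outcome with an effect size, a confidence level and a power, so it is the natural primary outcome. Third place in an unranked list proves nothing against that. The choice of tests, the handling of repeated pain scores and any multiplicity rule commonly sit in a statistical analysis plan, which may exist and is not shown.

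Much of this stands. A missing multiplicity method is not the complaint. Three stronger readings that a reader might infer should also be set aside:

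- That hypothesis, first objective and sample size rest on three different outcomes. The hypothesis names none, and block duration ends at nearly the same event as the sizing outcome.
- That the protocol commits itself to rejecting the null on any of 18 unadjusted tests. No passage says so.
- That the stated 95% confidence is false. It is attached only to time to first analgesic and is never claimed for the broad hypothesis.

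What the reply does not remove is the wording of the first objective. Hypothesis, objectives and sizing outcome are protocol content. Even if an analysis plan named time to first analgesic as primary, the protocol would still say that sensory block measures will show which block is better.

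**Conclusion.** The concern holds in a limited form. The hypothesis is tied to no outcome, none is designated primary, and the one sentence that says how the better block will be found uses measures on which the trial was not sized. The 95% and 80% figures cover time to first analgesic alone.

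The false-rejection figures (about 15% to 51% with 18 tests at correlations of 0.9 to 0.3) illustrate what the wording leaves open; they do not describe a stated procedure. They rest on unadjusted 5% tests, an any-one-suffices rule and assumed equal correlations. The 60% under independence is an upper figure that will not be reached, because repeated pain scores in the same patient, and block duration and time to rescue, are correlated. Even at a correlation of 0.9, or with only 8 tests, the rate stays above twice the nominal 5%. This should be corrected before analysis; it does not invalidate the design.

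**What to change.** By amendment before analysis:

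1. Restate H0 and H1 as a two-sided 5% comparison of Group E with Group S on time to first rescue analgesic.
2. List that objective first and name the outcome primary.
3. In the sensory block objective, delete the clause on detecting which block gives better analgesia.
4. Label sensory block onset, quality and duration, the 12 pain readings, fentanyl, morphine, satisfaction and all comparisons with Group C as secondary, and state that none of them alone suffices to reject H0.
5. Reconcile the pain-score triggers under Assessment of block (above 3) and Postoperative (equal to or above 3), so that the primary outcome has one definition.
6. Restate the power for the two-sided test: about 68% to 70% at 25 per group, not 80%.

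Cost: the rewording itself needs no new patients or data. A lone significant secondary result can no longer be claimed as the trial's answer. The power shortfall exists already but becomes explicit. Restoring 80% two-sided power on the protocol's inputs would take 32 per group (33 with the t distribution), that is 3 × 32 = 96 patients in place of 75; whether to enlarge the trial is a separate decision.

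### The stated inputs require 32 to 33 patients per block group, not 25; at 25 per group the power is about 68–70%, not 80%

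*Protocol*

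**What the plan says.** Under Technical design, Sample size, the protocol takes its assumptions on time to first analgesia from a published study: the mean in the "erector spinae block group is 416 ± 108.2 minute and that in serratus anterior block is 343 ± 99.7 minute". From these it says a sample size program gives a requirement "to be 75 cases (25 cases in each group) with confidence level of 95% and power of test 80" per cent. The paragraph does not say whether the test is one- or two-sided, and it gives no assumption for the control group.

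Two other places settle how the calculation should be read. The alternative hypothesis has no direction: "There is difference between Ultrasound-Guided Erector Spinae Plane Block and Serratus anterior plane Block in providing peri operative analgesia". Under Operational design, Randomization, allocation is equal: "A computer-generated table will be used to divide patients equally into 3 study groups", with 25 patients each in the erector spinae, serratus anterior and control groups.

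**The concern.** The paragraph gives both the inputs and the answer, so it can be recomputed directly, and the answer looks too small. The standardised difference is about 0.70 (73 min over a pooled SD of about 104 min). That normally calls for a little over 30 per group at two-sided 5% and 80% power.

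Erector spinae versus serratus anterior on time to first analgesia is the trial's research question and the only comparison given a sample size basis. If its power is overstated, the ethics committee and patients are told the trial has a better chance of answering its question than it has. A non-significant result would also be read with unwarranted confidence as showing no difference between the blocks.

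**Working it through.** **Inputs (all from the protocol)**

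- Erector spinae: mean 416, SD 108.2 min. Serratus anterior: mean 343, SD 99.7 min (Sample size).
- Difference: 416 − 343 = 73 min.
- Sum of variances: 108.2² + 99.7² = 11707.24 + 9940.09 = 21647.33. Pooled SD = √(21647.33/2) = 104.04 min.
- Confidence 95% and power 80% (Sample size). Two-sided, because the alternative hypothesis has no direction, so z = 1.960 and 0.842.
- Equal groups (Randomization).

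**Trying to reproduce 25 per group**

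n per group = (SD₁² + SD₂²)(z₁₋α/₂ + z_power)² / difference²

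= 21647.33 × (1.95996 + 0.84162)² / 5329 = 31.88, so **32 per group**.

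The t test needs 33: its power is 78.9% at 32 and 80.2% at 33.

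The stated 25 is not reproduced. The choice of SD does not explain the gap: using 99.7 for both groups gives 30, and using 108.2 for both gives 35. A common SD of 92.1 min would be needed to reach 25, which is below both stated values.

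**Power at 25 per group**

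- Standard error = √(21647.33/25) = 29.43 min.
- 73/29.43 = 2.481.
- Power = Φ(2.481 − 1.960) = **69.9%**. By the noncentral t it is **68.1%**.
- Difference detectable with 80% power = (1.960 + 0.842) × 29.43 = **82.4 min**, or 84.1 min by the t test.

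**Settings that come near 25 or 75**

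| Setting | Result | Conflict with the protocol |
|---|---|---|
| Two-sided 5%, 70% power | 25.07 per group | Power is stated as 80% |
| One-sided 5%, 80% power | 25.11 per group; power at 25 is 79.8% (normal) or 78.8% (t) | Alternative hypothesis has no direction |
| Two-sided 5%, 80% power, 2:1 allocation | 24.6 and 49.1, i.e. 25 + 50 = 75 | Equal allocation, 25 in each of three groups |

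The first two round up to 26 by the same rule that takes 31.88 to 32, so they match 25 only approximately.

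A three-group overall test cannot be checked, because no control mean is stated. With assumed control means of 379.5, 343 and 300 min it would need about 41, 31 and 17 per group. It would not in any case power the comparison of the two blocks named in the hypothesis.

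**The case against.** The strongest defence is that the Sample size paragraph names no sidedness, and a one-sided 5% test gives 25.1 per group with 79.8% power at 25, which is in effect the stated 80%. A 2:1 ratio also gives exactly 25 + 50 = 75. Either could be where the figure came from, though that is inference. Neither justifies it: the first contradicts the protocol's own alternative hypothesis and the second its own allocation. If either was intended, the text would still have to change.

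A second point is that the power figures presuppose a particular analysis, while the Results section promises only standard statistical methods. That is fair, and the condition is stated in the conclusion. It makes little difference: with the error variance pooled over all three groups (72 degrees of freedom, assuming a similar SD in controls), power is about 68.7%.

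Third, the shortfall neither biases the estimated difference nor inflates the type I error. That is true. The harm lies in an overstated chance of success and in how a null result would be read.

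The protocol also states no allowance for losses. Outcomes are collected within 24 hours of surgery and no loss rate is given, so this is not counted as an error here, although any loss would lower power further.

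**Conclusion.** The concern holds. On the protocol's own inputs, with a two-sided 5% test and equal groups, the requirement is 32 per group (33 by the t test). The stated 25 is short by 7 to 8 patients in each block group. Power for the assumed 73-minute difference is 69.9% (normal) or 68.1% (t), about 10 to 12 points below the claim. The risk of missing that difference is 30–32%, roughly one and a half times the stated 20%.

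These figures assume a two-sample comparison of means at an unadjusted 5% level, the stated means and SDs, and complete data on 25 patients per group. The sample size and its power are stated outright in the protocol, so this is an error on the page and not a detail left to a later analysis plan. It should be corrected.

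**What to change.** Restate the Sample size paragraph along these lines: *with 25 patients per group, a two-sided 5% test comparing the two blocks has about 70% power (68% by the t test) for a difference of 73 minutes, and 80% power for a difference of about 82 to 84 minutes.* This costs wording only and can be done at any stage; the price is a less favourable stated power.

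If 80% power for 73 minutes is to be kept, enrol at least 32, preferably 33, per group. With three equal groups that is 96 to 99 patients, or 21 to 24 more than planned.

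If a one-sided test or an unequal ratio was intended, say so, justify it, and bring the Hypothesis or Randomization section into line.

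Moving control patients into the block groups within the total of 75 is not an equivalent solution. For example, 32:32:11 reaches 80.1% by the normal approximation but only 78.9% by the t test. With equal SDs assumed, it raises the standard error of a block-versus-control comparison by a factor of √[(1/32 + 1/11)/(2/25)] = 1.24.

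### Intra-operative IV paracetamol is ordered at 15 ml/kg with no concentration, so no dose is fixed; very probably a slip for 15 mg/kg

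*Protocol*

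**What the plan says.** The protocol orders intravenous paracetamol twice.

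- **During surgery** (General anesthesia): "Paracetamol 15ml/kg will be administered by iv infusion to all patients". The order is by volume per kilogram and gives no strength. It belongs to a regimen described as standardized for every patient.
- **After surgery** (Postoperative): "All patients will receive paracetamol as standard intravenous infusion analgesia at dose of 15mg/Kg every 8 hours (maximum dose: 4 g / day"). The order is by mass per kilogram, with a daily ceiling.

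No section states a paracetamol concentration, and none explains why the two orders use different units.

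**The concern.** A volume per kilogram is a dose only when the strength of the solution is known. Without it, the intra-operative order leaves the mass of drug open. The number 15, the drug and the route are the same as in the post-operative order, and only the unit differs, which points to a writing error.

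Patient safety is at stake. The order applies to every participant (three groups of 25, so 75 patients). Whether a literal reading would do harm depends on a strength the protocol does not give. Because the order is identical in all arms, it does not favour one block over the other or over control, and it has no bearing on the sample size.

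**Working it through.** **Step 1: compare the unit with the protocol's other drug orders.**

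Orders scaled to body weight:

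| Drug | Section | Unit |
|---|---|---|
| Midazolam | Steps of Performance, Preparation | mg/kg |
| Fentanyl | General anesthesia | mcg/kg |
| Propofol | General anesthesia | mg/kg |
| Cisatracurium | General anesthesia | mg/kg |
| Neostigmine | General anesthesia | mg/kg |
| Atropine | General anesthesia | mg/kg |
| Morphine | Postoperative | mg/kg |
| Paracetamol, post-operative | Postoperative | mg/kg |
| **Paracetamol, intra-operative** | **General anesthesia** | **ml/kg** |

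Eight of these nine orders are in mass per kilogram. For example, induction reads "Fentanyl 2 mcg/kg, propofol 2 mg/kg will be intravenously administered, followed by cisatracurium 0.15 mg/kg to facilitate endotracheal intubation" and reversal reads "neostigmine (0.05 mg/kg) and atropine sulphate (0.01 mg/kg"). The intra-operative paracetamol order is the only one in ml/kg.

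Orders given by volume: bupivacaine 20 ml at 0.25% in each of the two blocks, lidocaine 3 ml at 1% for skin infiltration, and intra-operative paracetamol. Three of the four state a strength. Paracetamol does not.

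**Step 2: convert the order to a dose.**

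Dose per kg = 15 ml/kg × c mg/ml = 15c mg/kg, where c is the unstated concentration. Setting 15c = 15 mg/kg gives c = 1 mg/ml, the only strength at which the two paracetamol orders agree. No milligram dose can be reproduced from the protocol itself.

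**Step 3: show the range.**

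Assumptions: body weight of 60, 70 or 80 kg (the protocol limits only body mass index, to below 35 kg/m²) and c of 1, 5 or 10 mg/ml. Neither comes from the protocol.

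- Volume = 15 × weight.
- Dose = volume × c.
- Strength at which one infusion reaches 4 g = 4000 mg ÷ volume.

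| Weight | Volume | 1 mg/ml | 5 mg/ml | 10 mg/ml | Strength giving 4 g |
|---|---|---|---|---|---|
| 60 kg | 900 ml | 0.90 g | 4.50 g | 9.0 g | 4000/900 = 4.44 mg/ml |
| 70 kg | 1050 ml | 1.05 g | 5.25 g | 10.5 g | 4000/1050 = 3.81 mg/ml |
| 80 kg | 1200 ml | 1.20 g | 6.00 g | 12.0 g | 4000/1200 = 3.33 mg/ml |

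Per kilogram, the three strengths give 15, 75 and 150 mg/kg, which is 1, 5 and 10 times the post-operative dose.

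**Step 4: read the unit as mg.**

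15 mg/kg gives 0.90, 1.05 or 1.20 g at 60, 70 or 80 kg. Each single dose is the same as a post-operative dose and well under 4 g.

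**The case against.** - **The slip is easy to see.** If mg/kg is so clearly intended, an anaesthesiologist would recover it, and being asked to infuse about a litre of one drug would raise a query. That is fair: the multi-gram figures describe an improbable reading and are not a forecast of harm. But a dosing order should be right as written and should not rely on the person giving it to correct it.
- **The two orders cover different times.** This is true, so neither countermands the other; the inconsistency is one of unit. The defect does not depend on the post-operative order, because the intra-operative order alone fixes no dose.
- **A letter may have been misread when the PDF was converted to text.** This cannot be fully excluded, since the point turns on one character. The other mg/kg expressions, including the post-operative paracetamol order, came through correctly, so there is no positive evidence of a misreading. A glance at the original page settles it.
- **The 4 g/day ceiling is written into the post-operative order.** It is used above as a yardstick, and the protocol does not say whether it counts the intra-operative dose. If it does, it can matter even after the correction. One intra-operative and three post-operative doses within 24 hours total 4 × 15 = 60 mg/kg, which is 3.6, 4.2 or 4.8 g at 60, 70 or 80 kg. The stated maximum would then limit the total. This does not change the unit correction.

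**Conclusion.** The concern holds. As written, the intra-operative paracetamol order fixes no dose, and its unit is inconsistent with every other weight-based order in the protocol. That mg/kg was meant is an inference, but a strong one, resting on the same number, drug and route and on the mass units used everywhere else.

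Taken literally, the dose equals the post-operative one only at 1 mg/ml, and a single infusion passes 4 g at strengths above 3.33 to 4.44 mg/ml for assumed weights of 80 down to 60 kg. It should be corrected because it is an operative instruction for all patients. It has no consequence for bias between groups, power or analysis.

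**What to change.** Have the investigators confirm the intended dose, then change the unit in the General anesthesia section from ml/kg to mg/kg, so that it reads 15 mg/kg. If a volume is really intended, state the concentration beside it. It would also help to say whether the 4 g/day maximum includes the intra-operative dose.

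The cost is a one-unit protocol correction, with no change to the sample size, procedures or analysis.
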